- 3.1.10 Females of childbearing potential (FOCBP), must use appropriate method(s) of contraception. FOCBP are defined as those who are not surgically sterile (i.e., bilateral tubal ligation, bilateral oophorectomy, or complete hysterectomy) or postmenopausal (defined as 12 months with no menses without an alternative medical cause). Additionally, FOCBP must agree to follow instructions for method(s) of contraception for the duration of treatment with durvalumab plus 5 half-lives of durvalumab (13 weeks) plus 30 days (duration of ovulatory cycle) for a total of 17 weeks post-treatment completion (details in appendix).
- 3.1.11 Men who are sexually active with FOCBP must agree to follow instructions for method(s) of contraception for the duration of treatment with durvalumab plus 5 half-lives of durvalumab plus 90 days (duration of sperm turnover) for a total of 25 weeks post-treatment completion (details in appendix).
- 3.1.12 Provide written informed consent.
- 3.1.13 Ability to complete questionnaire(s) by themselves or with assistance.
- 3.1.14 Willingness to provide mandatory blood specimens for correlative research (see Section 14.0).
- 3.1.15 Willingness to provide mandatory tissue specimens for correlative research (see Section 17.0). **NOTE:** If tissue is deemed inaccessible, patient cannot participate in study.
- 3.1.16 Willingness to return to enrolling institution for follow-up (during the Active Monitoring Phase of the study).
- 3.1.17 Must have a life expectancy of at least 6 months.

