15.0 Drug Information

IND Exempt. See prescribing information for full information.

15.1 Durvalumab (MEDI4736, IMFINZI™):

15.1.1 **Background:** Durvalumab is a human immunoglobulin (Ig) G1 kappa (IgG1κ) monoclonal antibody (mAb) that blocks the interaction of programmed cell death ligand 1 (PD-L1) (but not programmed cell death ligand-2) with programmed cell death 1 (PD-1) on T-lymphocyte (T-cells) and cluster of differentiation (CD)80 (B7.1) on immune cells (IC) and is engineered to reduce antibody-dependent cell-mediated cytotoxicity (ADCC).

15.1.2 **Formulation:** Durvalumab will be supplied by AstraZeneca as a 500-mg vial solution for infusion after dilution. The solution contains 50 mg/mL durvalumab, 26 mM histidine/histidine hydrochloride, 275 mM trehalose dihydrate, and 0.02% weight/volume (w/v) polysorbate 80; it has a pH of 6.0 and density of 1.054 g/mL. The nominal fill volume is 10.0 mL. Investigational product vials are stored at 2°C to 8°C (36°F to 46°F) and must not be frozen. Drug product should be kept in original packaging until use to prevent prolonged light exposure.

15.1.3 **Preparation and storage:** Withdraw desired volume from vial and dilute in either 0.9% sodium chloride or 5% Dextrose in Water to a final concentration of 1 to 15 mg/mL. Total time from needle puncture of the durvalumab vial to the start of administration should not exceed 24 hours at 2°C to 8°C (36°F to 46°F) or 4 hours at room temperature. Infusion solution must be allowed to equilibrate to room temperature prior to commencement of administration.

15.1.4 **Administration:** Durvalumab is delivered through an IV administration set with a 0.2- or 0.22-micron filter. The standard infusion time is 1 hour. Do not co-administer other drugs through the same infusion line. Flush the IV line with a volume of IV diluent equal to the priming volume of the infusion set used after the contents of the IV bag are fully administered.

15.1.5 **Pharmacokinetic information:**

- **Volume of Distribution:** The mean volume of distribution at steady state was 5.6 liters
- **Half-life elimination:** The mean terminal half-life at steady state was approximately 18 days.
- **Excretion:** Mean steady state clearance was 8.2 mL/hr.

15.16 **Potential Drug Interactions:** Durvalumab is an immunoglobulin; therefore, no formal pharmacokinetic drug-drug interaction studies have been conducted.

15.17 **Known potential toxicities:**

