Appendix V: Restrictions for blood donation and for those of childbearing age

The following restrictions apply while the patient is receiving study treatment and for the specified times before and after:

Female patient of child-bearing potential

Female patients of childbearing potential who are not abstinent and intend to be sexually active with a non-sterilized male partner must use at least 1 **highly** effective method of contraception from the time of screening throughout the total duration of the drug treatment and the drug washout period (90 days after the last dose of durvalumab monotherapy). Non-sterilized male partners of a female patient of childbearing potential must use male condom plus spermicide throughout this period. Cessation of birth control after this point should be discussed with a responsible physician. Periodic abstinence, the rhythm method, and the withdrawal method are not acceptable methods of birth control. Female patients should also refrain from breastfeeding throughout this period.

Male patients with a female partner of childbearing potential

Non-sterilized male patients who are not abstinent and intend to be sexually active with a female partner of childbearing potential must use a male condom plus spermicide from the time of screening throughout the total duration of the drug treatment and the drug washout period (90 days after the last dose of durvalumab monotherapy). However, periodic abstinence, the rhythm method, and the withdrawal method are not acceptable methods of contraception. Male patients should refrain from sperm donation throughout this period.

Female partners (of childbearing potential) of male patients must also use a highly effective method of contraception throughout this period.

N.B Females of childbearing potential are defined as those who are not surgically sterile (i.e., bilateral salpingectomy, bilateral oophorectomy, or complete hysterectomy) or post-menopausal.

Women will be considered post-menopausal if they have been amenorrhoeic for 12 months without an alternative medical cause. The following age-specific requirements apply:

Women <50 years of age would be considered post-menopausal if they have been amenorrhoeic for 12 months or more following cessation of exogenous hormonal treatments and if they have luteinizing hormone and follicle-stimulating hormone levels in the post-menopausal range for the institution.

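### Appendix V ends contraception 90 days after the last durvalumab dose for both sexes, 29 days (women) and 85 days (men) earlier than inclusion criteria 3.1.10 and 3.1.11

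*Combined protocol and SAP*

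**What the plan says.** Three places in the combined protocol and SAP bear on this.

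- **Section 3.1, criterion 3.1.10 (women).** Contraception continues through durvalumab treatment and then for five half-lives, given as "13 weeks) plus 30 days (duration of ovulatory cycle) for a total of 17 weeks post-treatment completion (details in appendix").
- **Section 3.1, criterion 3.1.11 (men).** Contraception continues "for the duration of treatment with durvalumab plus 5 half-lives of durvalumab plus 90 days (duration of sperm turnover"), with the total given as "plus 90 days (duration of sperm turnover) for a total of 25 weeks post-treatment completion (details in appendix").
- **Appendix V.** It opens by saying that its "restrictions apply while the patient is receiving study treatment and for the specified times before and after". The women's paragraph and the men's paragraph then each run from screening, through treatment, to the end of "the drug washout period (90 days after the last dose of durvalumab monotherapy").

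The criteria do not number the appendix they refer to, but Appendix V is the only one that deals with contraception. Section 15.1.5 supplies the half-life: "The mean terminal half-life at steady state was approximately 18 days".

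The women's paragraph of Appendix V adds one sentence that the men's paragraph lacks: "Cessation of birth control after this point should be discussed with a responsible physician". Several further instructions in Appendix V refer back to the same 90-day period. They cover condom use by a female patient's partner ("Non-sterilized male partners of a female patient of childbearing potential must use male condom plus spermicide throughout this period"), breastfeeding, sperm donation, and contraception by a male patient's partner. Blood donation has its own 90-day rule.

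**The concern.** The criteria treat drug washout as insufficient by itself. They add an ovulatory cycle for women and a sperm-turnover period for men. Appendix V stops where the washout term stops. No text says which governs, and the criteria direct the reader to the appendix, so a coordinator who follows the cross-reference arrives at the shorter figure.

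At stake is a participant-protection instruction. Someone who counsels from Appendix V would release patients before the criteria do. Women keep two partial safeguards: the physician discussion, and the pregnancy tests that Section 4.1 schedules at the end-of-treatment visit and in follow-up. Men have neither, because their paragraph has no such sentence and the tests are for patients, not partners.

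**Working it through.** **Inputs.** Half-life of about 18 days (Section 15.1.5). Five half-lives plus 30 days, total 17 weeks (3.1.10). Five half-lives plus 90 days, total 25 weeks (3.1.11). 90 days for both sexes (Appendix V).

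**Step 1: reproduce the criteria.**
- Five half-lives: 5 × 18 = 90 days; 90 / 7 = 12.9 weeks. Criterion 3.1.10 gives 13.
- Women: 90 + 30 = 120 days; 120 / 7 = 17.1 weeks. Stated: 17 weeks = 17 × 7 = 119 days.
- Men: 90 + 90 = 180 days; 180 / 7 = 25.7 weeks. Stated: 25 weeks = 25 × 7 = 175 days.

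Both totals reproduce. The women's total is one day below its components, which is ordinary rounding. The men's total is rounded down by 180 − 175 = 5 days.

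**Step 2: identify what Appendix V contains.** Its 90 days equals 5 × 18 days exactly, and it calls the period washout. It therefore holds the first term of each criterion and omits the second.

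**Step 3: shortfall.**

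| | Criterion as stated | Appendix V | Shortfall | Shortfall against the unrounded sum |
|---|---|---|---|---|
| Women | 119 days | 90 days | 29 days (4.1 weeks) | 120 − 90 = 30 days |
| Men | 175 days | 90 days | 85 days (12.1 weeks) | 180 − 90 = 90 days |

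**Step 4: drug left at day 90.** (1/2)^5 = 1/32 = 3.1%. What is missing is the reproductive-cycle margin, not washout.

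**Step 5: when the male gap occurs.** Take nominal dosing, with the last dose at week 0 for dose level 1 and week 6 for dose level 4.
- Dose level 1: from week 0 + 12.9 = 12.9 to week 0 + 25 = 25 after Y90-RE.
- Dose level 4: from week 6 + 12.9 = 18.9 to week 6 + 25 = 31.

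These weeks are approximate. Visits have windows of ±5 days, and the second durvalumab dose may be given up to 5 days before Y90-RE (Section 4.1, footnote 9). In either case the gap falls after the end-of-treatment visit at week 8, during follow-up visits held at least every 3 months for 2 years (footnotes 12 and 13).

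**The case against.** The best defence is a division of labour: the criteria fix how long, and the appendix fixes which methods. Criterion 3.1.10 supports this in part, since it states the total outright and asks the patient to follow instructions on methods. It does not hold for Appendix V as written. The appendix says at the outset that it specifies times, and it then gives an end point in each paragraph.

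Other parts of the defence stand:

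- **The instructions are not incompatible.** A reader might infer that patients cannot comply with both. They can: whoever follows the longer period also meets the shorter one. The defect is a minimum set too low in the appendix.
- **The harm is conditional.** It requires staff to take the period from Appendix V and overlook the criterion. Patients remain in contact after week 8, although the follow-up visits list no contraception review.
- **Patients may have been told the right period.** A reader might infer that they were told 90 days. The consent pages are not in the public documents, so this cannot be judged either way.
- **Substantial drug exposure is not shown.** A reader might infer that contraception ends while much durvalumab remains. On the stated half-life about 3% is left at day 90, and the documents give no risk figure for the interval that follows.
- **Sperm donation and the female partner's contraception are a separate matter.** A reader might infer that 3.1.11 already requires 25 weeks for these. It mentions neither; both rest only on the 90-day period in Appendix V. Extending them is consistent with the sperm-turnover rationale, but it would be a new requirement.

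**Conclusion.** The inconsistency is real and lies in current text. Appendix V understates the contraception period by 29 days for women and 85 days for men, because it carries the five-half-life term and drops the sex-specific margin. The exposure is limited to counselling taken from Appendix V, and it falls mainly on male patients and their partners.

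Severity is minor to moderate. At most 18 patients will be enrolled, at one site, and the documents do not say to how many the rules would apply. Sample size, dose escalation and analysis are unaffected.

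This conclusion rests on three assumptions: that the appendix the criteria point to is Appendix V; that the criteria's post-treatment period counts from the last durvalumab dose, as their wording on durvalumab treatment indicates; and that the half-life is about 18 days. The 29-day and 85-day figures do not depend on the half-life, because they compare stated totals. Only the reading of 90 days as washout alone does.

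**What to change.** In Appendix V, replace the whole phrase "the drug washout period (90 days after the last dose of durvalumab monotherapy"), including its label, with:

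- women: *for 17 weeks after the last dose of durvalumab (5 half-lives plus 30 days)*
- men: *for 25 weeks after the last dose of durvalumab (5 half-lives plus 90 days)*

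Changing only the figure in parentheses would leave a 17- or 25-week period described as washout, which it is not.

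Two decisions belong to the sponsor:

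1. **Rounding for men.** The stated components sum to 180 days and 25 weeks is 175. Using 26 weeks (26 × 7 = 182 days) in both 3.1.11 and Appendix V would cover them in full.
2. **Linked restrictions.** Breastfeeding, sperm donation and partners' contraception are tied to the period being changed, so they would lengthen unless addressed. State the period for each. Applying the male period to sperm donation and to the female partner follows the sperm-turnover rationale, but 3.1.11 does not require it.

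Leave the 90-day blood-donation rule as it is.

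The cost is a wording amendment to Appendix V, plus one figure in 3.1.11 if 26 weeks is adopted. The patients' appendix periods lengthen by 29 days (women) and 85 days (men), which the criteria already require. With 26 weeks, the men's appendix period lengthens by 182 − 90 = 92 days, and criterion 3.1.11 itself by 7 days. Any extension for partners, breastfeeding or sperm donation depends on the sponsor's choice under the second decision.

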Diagram 2

TheraSphere® Administration Accessory Kit
(shown assembled with TheraSphere® Administration Set)

[figure not shown]
[figure not shown]
[figure not shown]

Diagram 1

[figure not shown]
[figure not shown]
TheraSphere® Administration Set

Items in dashed boxes are not supplied with the Administration Set

Diagram 3
Illustration of the Plunger Assembly Inserted into the Dose Vial in the Acrylic Shield

K120615-023

28

Rev. 14

(pages 29 through 32 of the USPI are blank and are not added here)

Appendix VII: Dosing Modification and Toxicity Management Guidelines

Immune-Mediated, Infusion-Related, and Non-Immune-Mediated Reactions

Dose Modifications	Toxicity Management

Drug administration modifications of study drug/study regimen will be made to manage potential immune-related AEs based on severity of treatment-emergent toxicities graded per CTCAE v5.0. In addition to the criteria for permanent discontinuation of study drug/study regimen based on CTC grade/severity (below), permanently discontinue study drug/study regimen for the following conditions:
 
 – Inability to reduce corticosteroid to a dose of ≤ 10 mg of prednisone per day (or equivalent) within 12 weeks after last dose of study drug/study regimen – Recurrence of a previously experienced Grade 3 treatment-related AE following resumption of dosing 
Grade 1: No dose modification
 
Grade 2:
 
 – Hold study drug/study regimen dose until Grade 2 resolution to Grade ≤ 1. – If toxicity worsens, then treat as Grade 3 or Grade 4. – Study drug/study regimen can be resumed once event stabilizes to Grade ≤ 1 after completion of steroid taper. – Patients with endocrinopathies who may require prolonged or continued steroid replacement can be retreated with study drug/study regimen on the following conditions: 
 • The event stabilizes and is controlled. • The patient is clinically stable as per Investigator or treating physician's clinical judgement. • Doses of prednisone are at ≤ 10 mg/day or equivalent. 
Grade 3:
 
 – Depending on the individual toxicity, study drug/study regimen may be permanently discontinued. Please refer to guidelines below. 
Grade 4:
 
 – Permanently discontinue study drug/study regimen. 
Note: For asymptomatic amylase or lipase levels of $>2X$ ULN, hold study drug/study regimen, and if complete work up shows no evidence of pancreatitis, study drug/study regimen may be continued or resumed.
 
Note: Study drug/study regimen should be permanently discontinued in Grade 3 events with high likelihood for morbidity and/or mortality – e.g., myocarditis, or other similar events even if they are not currently noted in the guidelines. Similarly, consider whether study drug/study regimen should be permanently discontinued in Grade 2 events with high likelihood for morbidity and/or mortality – e.g., myocarditis, or other similar events even if they are not currently noted in the guidelines – when they do not rapidly improve to Grade <1 upon treatment with systemic steroids and following full taper
 
Note: There are some exceptions to permanent discontinuation of study drug for Grade 4 events (i.e., hyperthyroidism, hypothyroidism, Type 1 diabetes mellitus and also liver function tests as noted earlier in the protocol).
	
It is recommended that management of immune-mediated adverse events (imAEs) follows the guidelines presented in this table:
 
 – It is possible that events with an inflammatory or immune mediated mechanism could occur in nearly all organs, some of them not noted specifically in these guidelines. – Whether specific immune-mediated events (and/or laboratory indicators of such events) are noted in these guidelines or not, patients should be thoroughly evaluated to rule out any alternative etiology (e.g., disease progression, concomitant medications, and infections) to a possible immune-mediated event. In the absence of a clear alternative etiology, all such events should be managed as if they were immune related. General recommendations follow. – Symptomatic and topical therapy should be considered for low-grade (Grade 1 or 2, unless otherwise specified) events. – For persistent (>3 to 5 days) low-grade (Grade 2) or severe (Grade ≥ 3) events, promptly start prednisone 1 to 2 mg/kg/day PO or IV equivalent. – Some events with high likelihood for morbidity and/or mortality – e.g., myocarditis, or other similar events even if they are not currently noted in the guidelines – should progress rapidly to high dose IV corticosteroids (methylprednisolone at 2 to 4 mg/kg/day) even if the event is Grade 2, and if clinical suspicion is high and/or there has been clinical confirmation. Consider, as necessary, discussing with the study physician, and promptly pursue specialist consultation. – If symptoms recur or worsen during corticosteroid tapering (28 days of taper), increase the corticosteroid dose (prednisone dose [e.g., up to 2 to 4 mg/kg/day PO or IV equivalent]) until stabilization or improvement of symptoms, then resume corticosteroid tapering at a slower rate (>28 days of taper). – More potent immunosuppressives such as TNF inhibitors (e.g., infliximab) (also refer to the individual sections of the imAEs for specific type of immunosuppressive) should be considered for events not responding to systemic steroids. Progression to use of more potent immunosuppressives should proceed more rapidly in events with high likelihood for morbidity and/or mortality – e.g., myocarditis, or other similar events even if they are not currently noted in the guidelines – when these events are not responding to systemic steroids. – With long-term steroid and other immunosuppressive use, consider need for Pneumocystis jirovecii pneumonia (PJP, formerly known as Pneumocystis carinii pneumonia) prophylaxis, gastrointestinal protection, and glucose monitoring. – Discontinuation of study drug/study regimen is not mandated for Grade 3/Grade 4 inflammatory reactions attributed to local tumor response (e.g., inflammatory reaction at sites of metastatic disease and lymph nodes). Continuation of study drug/study regimen in this situation should be based upon a benefit-risk analysis for that patient.

Specific Immune-Mediated Reactions

Severity (CTCAE v 5.0)	Dose Modifications	Toxicity Management
Pneumonitis/Interstitial Lung Disease (ILD)		
Any	General Guidance	
 Monitor patients for signs and symptoms of pneumonitis or ILD (new onset or worsening shortness of breath or cough). Patients should be evaluated with imaging and pulmonary function tests, including other diagnostic procedures as described below. Initial work-up may include clinical evaluation, monitoring of oxygenation via pulse oximetry (resting and exertion), laboratory work-up, and high- resolution CT scan.
Grade 1 (asymptomatic, clinical, radiographic, or diagnostic observations only; intervention not indicated)	No dose modifications required. However, consider holding study drug/study regimen dose as clinically appropriate and during diagnostic work-up for other etiologies.	
 Monitor and closely follow up in 2 to 4 days for clinical symptoms, pulse oximetry (resting and exertion), and laboratory work-up and then as clinically indicated. Consider Pulmonary and Infectious disease consult.
Grade 2 (symptomatic; medical intervention indicated; limiting instrumental ADL)	
 Hold study drug/study regimen dose until resolution to Grade ≤ 1. If toxicity worsens, then treat as Grade 3 or Grade 4. If toxicity improves to Grade ≤ 1, then the decision to reinitiate study drug/study regimen will be based upon treating physician's clinical judgment and after completion of steroid taper. 	
 Monitor symptoms daily and consider hospitalization. Promptly start systemic steroids (e.g., prednisone 1 to 2 mg/kg/day PO or IV equivalent). Reimage as clinically indicated. If no improvement within 3 to 5 days, additional workup should be considered and prompt treatment with IV methylprednisolone 2 to 4 mg/kg/day started If still no improvement within 3 to 5 days despite IV methylprednisolone at 2 to 4 mg/kg/day, promptly start immunosuppressive therapy such as TNF inhibitors (e.g., infliximab at 5 mg/kg every 2 weeks). Caution: It is important to rule out sepsis and refer to infliximab label for general guidance before using infliximab. Once the patient is improving, gradually taper steroids over ≥ 28 days and consider prophylactic antibiotics, antifungals, or anti-PJP treatment (refer to current NCCN guidelines for treatment of cancer-related infections [Category 2B recommendation])^a Consider pulmonary and infectious disease consult. Consider, as necessary, discussing with study physician.
Grade 3 or 4 Grade 3: severe symptoms; limiting self-care ADL; oxygen indicated Grade 4: life-threatening respiratory compromise; urgent intervention indicated [e.g., tracheostomy or intubation]	Permanently discontinue study drug/study regimen.	
 Promptly initiate empiric IV methylprednisolone 1 to 4 mg/kg/day or equivalent. Obtain Pulmonary and Infectious disease consult; consider, as necessary, discussing with study physician. Hospitalize the patient. Supportive care (e.g., oxygen). If no improvement within 3 to 5 days, additional workup should be considered and prompt treatment with additional immunosuppressive therapy such as TNF inhibitors (e.g., infliximab at 5 mg/kg every 2 weeks' dose) started. Caution: rule out sepsis and refer to infliximab label for general guidance before using infliximab.

Severity (CTCAE v 5.0)	Dose Modifications	Toxicity Management
Diarrhea / Colitis		
Any Grade	General Guidance	
 Once the patient is improving, gradually taper steroids over ≥ 28 days and consider prophylactic antibiotics, antifungals, and, in particular, anti-PJP treatment (refer to current NCCN guidelines for treatment of cancer-related infections [Category 2B recommendation]).^a
Grade 1	No dose modifications.	
 Monitor for symptoms that may be related to diarrhea/enterocolitis (abdominal pain, cramping, or changes in bowel habits such as increased frequency over baseline or blood in stool) or related to bowel perforation (such as sepsis, peritoneal signs, and ileus). Patients should be thoroughly evaluated to rule out any alternative etiology (e.g., disease progression, other medications, or infections), including testing for Clostridium difficile toxin, etc. Steroids should be considered in the absence of clear alternative etiology, even for low-grade events, in order to prevent potential progression to higher grade event. Use analgesics carefully; they can mask symptoms of perforation and peritonitis. Monitor closely for worsening symptoms. Consider symptomatic treatment, including hydration, electrolyte replacement, dietary changes (e.g., American Dietetic Association colitis diet), and loperamide. Use probiotics as per treating physician's clinical judgment.
Grade 2	Hold study drug/study regimen until resolution to Grade ≤ 1	
 If toxicity worsens, then treat as Grade 3 or Grade 4. If toxicity improves to Grade ≤ 1, then study drug/study regimen can be resumed after completion of steroid taper. Consider symptomatic treatment, including hydration, electrolyte replacement, dietary changes (e.g., American Dietetic Association colitis diet), and loperamide and/or budesonide. Promptly start prednisone 1 to 2 mg/kg/day PO or IV equivalent. If event is not responsive within 3 to 5 days or worsens despite prednisone at 1 to 2 mg/kg/day PO or IV equivalent, GI consult should be obtained for consideration of further workup, such as imaging and/or colonoscopy, to confirm colitis and rule out perforation, and prompt treatment with IV methylprednisolone 2 to 4 mg/kg/day started. If still no improvement within 3 to 5 days despite 2 to 4 mg/kg IV methylprednisolone, promptly start immunosuppressives such as infliximab at 5 mg/kg once every 2 weeks^a. Caution: it is important to rule out bowel perforation and refer to infliximab label for general guidance before using infliximab. Consider, as necessary, discussing with study physician if no resolution to Grade ≤ 1 in 3 to 4 days. Once the patient is improving, gradually taper steroids over ≥ 28 days and consider prophylactic antibiotics, antifungals, and anti-PJP treatment (refer to current NCCN guidelines for treatment of cancer-related infections [Category 2B recommendation]).^a

Severity (CTCAE v 5.0)	Dose Modifications	Toxicity Management
Grade 3 or 4		
Grade 3 diarrhea: stool frequency of ≥ 7 over baseline per day; limiting self-care ADL	Grade 3 Permanently discontinue study drug/study regimen for Grade 3 if toxicity does not improve to Grade ≤ 1 within 14 days; study drug/study regimen can be resumed after completion of steroid taper.	
 Promptly initiate empiric IV methylprednisolone 2 to 4 mg/kg/day or equivalent. Monitor stool frequency and volume and maintain hydration. Urgent GI consult and imaging and/or colonoscopy as appropriate. If still no improvement within 3 to 5 days of IV methylprednisolone 2 to 4 mg/kg/day or equivalent, promptly start further immunosuppressives (e.g., infliximab at 5 mg/kg once every 2 weeks). Caution: Ensure GI consult to rule out bowel perforation and refer to infliximab label for general guidance before using infliximab. Once the patient is improving, gradually taper steroids over ≥ 28 days and consider prophylactic antibiotics, antifungals, and anti-PJP treatment (refer to current NCCN guidelines for treatment of cancer-related infections [Category 2B recommendation]).^a
Grade 4 diarrhea: life threatening consequences	Grade 4 Permanently discontinue study drug/study regimen.	
Grade 3 colitis: severe abdominal pain, fever; ileus; peritoneal signs		
Grade 4 colitis: life-threatening consequences, urgent intervention indicated		

Hepatitis (elevated LFTs) Infliximab should not be used for management of immune-related hepatitis

Any elevation in AST, ALT or TBIL (i.e., $> \text{ULN}$)	General Guidance	
 Monitor and evaluate liver function test: AST, ALT, ALP, and TB. Evaluate for alternative etiologies (e.g., viral hepatitis, disease progression, concomitant medications).
Grade 1 AST, ALT, or TBIL AST or ALT $> \text{ULN} \times 3 \text{ ULN}$ and/or TBIL $> \text{ULN} - 1.5 \times \text{ULN}$	
 No dose modifications. If it worsens, then treat as described for elevations in the row below. 	Continue LFT monitoring per protocol.
Grade 2 AST, ALT, or TBIL AST or ALT $> 3.0 - 5 \times \text{ULN}$ and/or TBIL $> 1.5 - 3 \times \text{ULN}$	
 Hold study drug/study regimen dose until resolution to AST or ALT $\leq 3.0 \times \text{ULN}$ and/or TB $\leq 1.5 \times \text{ULN}$. If toxicity worsens, then treat as described for elevations in the row below. If toxicity improves to AST or ALT $\leq 3.0 \times \text{ULN}$ and/or TB $\leq 1.5 \times \text{ULN}$, or baseline, resume study drug/study regimen after completion of steroid taper. 	
 Regular and frequent checking of LFTs (e.g., every 1 to 2 days) until elevations of these are improving or resolved. If no resolution to AST or ALT $\leq 3.0 \times \text{ULN}$ and/or TB $\leq 1.5 \times \text{ULN}$ in 1 to 2 days, consider, as necessary, discussing with study physician. If event is persistent (> 3 to 5 days) or worsens, promptly start prednisone 1 to 2 mg/kg/day PO or IV equivalent. If still no improvement within 3 to 5 days despite 1 to 2 mg/kg/day of prednisone PO or IV equivalent, consider additional work up and start prompt treatment with IV methylprednisolone 2 to 4 mg/kg/day. If still no improvement within 3 to 5 days despite 2 to 4 mg/kg/day of IV methylprednisolone, promptly start immunosuppressives (i.e., mycophenolate mofetil).^a Disyycess with study physician if mycophenolate mofetil is not available. Infliximab should NOT be used. Once the patient is improving, gradually taper steroids over ≥ 28 days and consider prophylactic antibiotics, antifungals, and anti-PJP treatment (refer to current NCCN guidelines for treatment of cancer-related infections [Category 2B recommendation]).^a
AST or ALT $> 5.0 \times \text{ULN}$ and/or	For elevations in transaminases $\leq 8 \times \text{ULN}$ or elevations in TBIL $\leq 5 \times \text{ULN}$:	
 Promptly initiate empiric IV methylprednisolone at 1 to 4 mg/kg/day or equivalent. If still no improvement within 3 to 5 days despite 1 to 4 mg/kg/day methylprednisolone IV or equivalent, promptly start treatment with

Severity (CTCAE v 5.0)	Dose Modifications	Toxicity Management
TBIL $>3.0 \times$ ULN	
 Hold study drug/study regimen dose until resolution to AST or ALT $\leq 3.0 \times$ ULN and/or TB $\leq 1.5 \times$ ULN, or baseline Resume study drug/study regimen if elevations downgrade to AST or ALT $\leq 3.0 \times$ ULN and/or TB $\leq 1.5 \times$ ULN, or baseline within 14 days and after completion of steroid taper. Permanently discontinue study drug/study regimen if the elevations do not downgrade to AST or ALT $\leq 3.0 \times$ ULN and/or TB $\leq 1.5 \times$ ULN or baseline within 14 days. 
For elevations in transaminases $>8 \times$ ULN or elevations in bilirubin $>5 \times$ ULN, permanently discontinue study drug/study regimen.
 
Permanently discontinue study drug/study regimen for any case meeting Hy's law criteria (AST and/or ALT $>3 \times$ ULN + bilirubin $>2 \times$ ULN without initial findings of cholestasis (i.e., elevated alkaline phosphatase) and in the absence of any alternative cause.^b Note that this does not apply to the week 2 (cycle 3) post Y90-RE when this is usually seen and subsides in the upcoming weeks (cycle 4). Also for those with Gilbert's syndrome, would need to rely on AST/ALT rather than total bilirubin.
	
 immunosuppressive therapy (i.e., mycophenolate mofetil). Discuss with study physician if mycophenolate is not available. Infliximab should NOT be used. Perform hepatology consult, abdominal workup, and imaging as appropriate. Once the patient is improving, gradually taper steroids over ≥ 28 days and consider prophylactic antibiotics, antifungals, and anti-PJP treatment (refer to current NCCN guidelines for treatment of cancer-related infections [Category 2B recommendation]).^a

Nephritis or renal dysfunction (elevated serum creatinine)

Any Grade	General Guidance	
		
 Consult with nephrologist. Monitor for signs and symptoms that may be related to changes in renal function (e.g., routine urinalysis, elevated serum BUN and creatinine, decreased creatinine clearance, electrolyte imbalance, decrease in urine output, or proteinuria). Patients should be thoroughly evaluated to rule out any alternative etiology (e.g., disease progression or infections). Steroids should be considered in the absence of clear alternative etiology even for low-grade events (Grade 2), in order to prevent potential progression to higher grade event.
Grade 1 (serum creatinine $>$ ULN to $1.5 \times$ ULN)	No dose modifications.	
Monitor serum creatinine weekly and any accompanying symptoms.
 
 If creatinine returns to baseline, resume its regular monitoring per study protocol. If creatinine worsens, depending on the severity, treat as Grade 2, 3, or 4. Consider symptomatic treatment, including hydration, electrolyte replacement, and diuretics. If baseline serum creatinine is elevated above normal, and there is a rise to > 1 to $1.5 \times$ baseline, consider following recommendations in this row.

Severity (CTCAE v 5.0)	Dose Modifications	Toxicity Management
Grade 2 (serum creatinine >1.5 to $3.0 \times$ baseline; >1.5 to $3.0 \times$ ULN)	
 Hold study drug/study regimen until resolution to Grade ≤ 1 or baseline. If toxicity worsens, then treat as Grade 3 or 4. If toxicity improves to Grade ≤ 1 or baseline, then resume study drug/study regimen after completion of steroid taper. 	
 Consider symptomatic treatment, including hydration, electrolyte replacement, and diuretics. Carefully monitor serum creatinine every 2 to 3 days and as clinically warranted. Consult nephrologist and consider renal biopsy if clinically indicated. If event is persistent (>3 to 5 days) or worsens, promptly start prednisone 1 to 2 mg/kg/day PO or IV equivalent. If event is not responsive within 3 to 5 days or worsens despite prednisone at 1 to 2 mg/kg/day PO or IV equivalent, additional workup should be considered and prompt treatment with IV methylprednisolone at 2 to 4 mg/kg/day started. Once the patient is improving, gradually taper steroids over ≥ 28 days and consider prophylactic antibiotics, antifungals, and anti-PJP treatment (refer to current NCCN guidelines for treatment of cancer-related infections [Category 2B recommendation]).^a When event returns to baseline, resume study drug/study regimen and routine serum creatinine monitoring per study protocol.
Grade 3 or 4 Grade 3: serum creatinine $>3.0 \times$ baseline; >3.0 to $6.0 \times$ ULN; Grade 4: serum creatinine $>6.0 \times$ ULN	Permanently discontinue study drug/study regimen.	
 Carefully monitor serum creatinine on daily basis. Consult nephrologist and consider renal biopsy if clinically indicated. Promptly start prednisone 1 to 2 mg/kg/day PO or IV equivalent. If event is not responsive within 3 to 5 days or worsens despite prednisone at 1 to 2 mg/kg/day PO or IV equivalent, additional workup should be considered and prompt treatment with IV methylprednisolone 2 to 4 mg/kg/day started. Once the patient is improving, gradually taper steroids over ≥ 28 days and consider prophylactic antibiotics, antifungals, and anti-PJP treatment (refer to current NCCN guidelines for treatment of cancer-related infections [Category 2B recommendation]).^a
Rash (excluding bullous skin formations)		
Any Grade (refer to NCI CTCAE v 5.0 for definition of severity/grade depending on type of skin rash)	General Guidance	
 Monitor for signs and symptoms of dermatitis (rash and pruritus). IF THERE IS ANY BULLOUS FORMATION, THE STUDY PHYSICIAN SHOULD BE CONTACTED AND STUDY DRUG DISCONTINUED.
Grade 1	No dose modifications.	
 Consider symptomatic treatment, including oral antipruritics (e.g., diphenhydramine or hydroxyzine) and topical therapy (e.g., urea cream).
Grade 2	
 For persistent (>1 to 2 weeks) Grade 2 events, hold scheduled study drug/study regimen until resolution to Grade ≤ 1 or baseline. If toxicity worsens, then treat as Grade 3. If toxicity improves to Grade ≤ 1 or baseline, then resume 	
 Obtain dermatology consult. Consider symptomatic treatment, including oral antipruritics (e.g., diphenhydramine or hydroxyzine) and topical therapy (e.g., urea cream). Consider moderate-strength topical steroid.
		
 If no improvement of rash/skin lesions occurs within 3 to 5 days or is worsening

Severity (CTCAE v 5.0)	Dose Modifications	Toxicity Management
Grade 3 or 4	For Grade 3:	
consider, as necessary, discussing with study physician and promptly start systemic steroids such as prednisone 1 to 2 mg/kg/day PO or IV equivalent. If > 30% body surface area is involved, consider initiation of systemic steroids sooner.
 
 Consider skin biopsy if the event is persistent for >1 to 2 weeks or recurs.

Grade 3 or 4	For Grade 4 (or life-threatening):	
 Hold study drug/study regimen until resolution to Grade ≤ 1 or baseline. Consider dermatology. Promptly initiate empiric IV methylprednisolone 1 to 4 mg/kg/day or equivalent. Consider hospitalization.
--------------	------------------------------------	---

Grade 3 or 4	If temporarily holding the study drug/study regimen does not provide improvement of the Grade 3 skin rash to Grade ≤ 1 or baseline within 30 days, then permanently discontinue study drug/study regimen.	
 Monitor extent of rash [Rule of Nines].
--------------	--	---

Grade 3 or 4	Permanently discontinue study drug/study regimen.	
 Consider skin biopsy (preferably more than 1) as clinically feasible. Once the patient is improving, gradually taper steroids over ≥ 28 days and consider prophylactic antibiotics, antifungals, and anti-PJP treatment (refer to current NCCN guidelines for treatment of cancer-related infections [Category 2B recommendation]).^a Consider, as necessary, discussing with study physician.
--------------	---	--

Endocrinopathy

hyperthyroidism, hypothyroidism, Type 1 diabetes mellitus, hypophysitis, hypopituitarism, and adrenal insufficiency; exocrine event of amylase/lipase increased included in this section

